Unless otherwise stated, the criteria of evaluation will be the same in children as in adults. QoL will be reported descriptively. For the primary endpoint of safety, all adverse events will be coded according to MedDRA preferred term and reported and graded using the NCI CTCAE v4. For the safety assessment, a dose limiting toxicity (DLT) will be defined as any grade 3 or 4 adverse event that is attributed to ABT-414, or an ABT-414 toxicity that results in a delay of the second dose of ABT-414 by more than 14 days.

Statistical considerations:

There will be no maximum enrollment for children with HGG and EGFR amplification; however it is expected that at least 6 subjects will be enrolled. A dose in children where there are 1 or fewer dose limiting toxicities (DLTs) is expected to be determined. Given the small expected sample size, the pharmacokinetic profile, safety assessments, and efficacy evaluations, including neurological status and PedsQL™ Cancer Module Questionnaires will be summarized descriptively.

Kaplan-Meier survival curve will be estimated for overall survival. Joint Kaplan-Meier survival plots with matched historical patients at least from Korshunov (2015) (Ref. 40) will also be presented.

Pharmacokinetic parameters of ABT-414 and Cys-mcMMAF will be determined by noncompartmental methods. Individual pharmacokinetic parameters will be listed and summarized. The pediatric pharmacokinetic data may be analysed with adult pharmacokinetic data from other studies in a non-linear mixed effects modelling to estimate population pharmacokinetic parameters of ABT-414 and cys-mcMMAF, such as clearance and volume of distribution. The effect of demographic and/or disease-specific variable(s) on the pharmacokinetic parameters of ABT-414 and cys-mcMMAF will also be examined.

Assuming the same PK variability as in adults, ≥ 6 pediatric subjects will yield a two-sided 95% confidence interval within 60% and 140% of the geometric mean estimate for the area under the concentration-time curve (AUC) with greater than 90% probability. This criteria follows FDA draft guidance on the General Clinical Pharmacology Considerations for Pediatric Studies (released Dec 2014).

For a sample size of 6 in HGG with EGFR amplification, the probability of observing at least 1 tumor response will be 82.2% if the true response rate is 25%.

Response rate	Probability of observing 1 or more tumor responses		
	Sample size N = 6	Sample size N = 9	Sample size N = 12
15%	62.3%	76.8%	85.8%
20%	73.8%	86.6%	93.1%
25%	82.2%	92.5%	96.8%

All subjects who receive at least one dose of ABT-414 will be included in analyses. No interim analysis is planned.

Data Monitoring:

The EORTC and sponsor study teams will have open access to pediatric data throughout the study to inform the ongoing conduct of this open-label sub-study. EORTC will identify at least three individuals (a statistician, the PI, and a clinician from headquarters) that will review the safety events from the pediatric patients at the following timepoints: 4 weeks after each subject is enrolled and again at q4-6 month intervals while there are subjects that remain on therapy. If there are no subjects on active therapy, then the EORTC will not hold pediatric safety reviews.

Otherwise, data monitoring will be the same as specified for the adult population (refer to Chapter 9). Pediatric data will be analyzed separately from the adult study, but findings will be compared to those from the adult study. Pediatric data will not be included in the efficacy and safety analyses of the adult main study.

Translational research:

Tumor specimens will be collected where feasible for the same biomarker analyses that are planned for the adult population. Central molecular testing will include but not be limited to EGFR, H3.1, H3.3, BRAF, CDKN2A/B, IDH1, INI1, MGMT, PTEN. Insufficient tissue for Translational Research after EGFR amplification analysis will not prevent enrollment of the pediatric patients.

Forms and procedures for collecting data:

Data will be reported on the forms specifically designed by the EORTC Headquarters for this pediatric sub-study. Forms will be sent electronically to the EORTC Headquarters through the VISTA/RDC (Remote Data Capture System) as outlined in Chapter 14 of the adult protocol.

Informed consent:

Subjects and/or their legal guardians must be able to understand the risks and potential benefits and grant assent/consent to participate by signing a pediatric-specific informed assent/consent form(s) as per local and country specific laws and regulations.

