proportional. ABT-414 serum exposure was moderately lower than that of total ABT-806. In M13-379, for dose-normalized C_{max}, cys-mcMMAF was approximately 400 -fold lower than that of ABT-414 in molar concentration. The observed harmonic mean terminal phase elimination half-life ranged approximately from 7.5 to 12 days and 9 to 15 days for ABT-414 and total ABT-806, respectively. The observed mean clearance of ABT-414 ranged approximately from 0.19 to 0.37 mL/h/kg. The observed harmonic mean terminal phase elimination half-life of cys-mcMMAF was approximately 4 days.

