To assess if there would be any additional toxicity of ABT-414 on patients aged under 3 years (compared to what is already known from the adult toxicity profile), Juvenile CrI:CD1(ICR) mice were administered 5, 25, or 50 mg/kg/dose ABT-414 once every two weeks from Postnatal Day (PND) 7 to 70, followed by a 98 day non-dosing recovery phase. ABT-414 administered to juvenile mice once every 2 weeks from Post Natal Day (PND) 7 to 70 was associated with adverse histological effects in the testes, lung, ovaries and heart at ≥ 5 mg/kg. Therefore, a no-observed-adverse-effect-level (NOAEL) for ABT-414 in juvenile mice was not established, and was determined to be < 5 mg/kg (PND 63 Conjugated Antibody AUC of 15400 $\mu\text{g}\cdot\text{hr}/\text{mL}$). In addition, the overall systemic exposure to ABT-414 and its toxicity profile in this repeat dose juvenile mouse toxicity study was comparable to the toxicity profile observed in repeat dose adult mouse toxicity studies, and no new or unexpected toxicities were observed. Therefore, following the completion of the mouse study, the pediatric sub-study was opened to include patients aged under 3 years.

Allowing investigator discretion to use ABT-414 as monotherapy or in combination with temozolomide (informed by factors such as patient preference and prior exposure to temozolomide) minimizes barriers to subject inclusion, and it is reasonable to extrapolate from adult data that variable temozolomide use in children receiving ABT-414 will not affect the ability to assess pharmacokinetic or safety objectives of this sub-study. The use of TMZ in combination with ABT-414 for a pediatric patient must be reviewed by the EORTC/AbbVie medical monitor prior to the initiation of therapy. The safety profile of ABT-414 in combination with other anti-neoplastic agents has not been assessed to date.

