This appendix will describe the evaluation of pharmacokinetics, safety and efficacy of ABT-414 in the pediatric HGG population, allowing access to a novel therapy for those who are in great need of better treatment options. Subjects < 18 years of age with pediatric HGG whose tumors demonstrate EGFR amplification will be assigned to this pediatric sub-study. Pediatric subjects will receive open-label ABT-414 at a dose of 1.0 mg/kg for subjects who are 6 to 17 years old (at the date of first ABT-414 dose), or 1.3 mg/kg for subjects who are 0 to 5 years old. These dosages are expected to produce pharmacokinetic drug exposures comparable to a 1.0 mg/kg dose in adults, the recommended starting dose for the adult portion of the study.

Objectives of the sub-study

The primary objectives will be the evaluation of safety, tolerability and pharmacokinetics of ABT-414 in a pediatric population < 18 years of age. The secondary objective will be to assess the effect of ABT-414 on tumor response per RANO (Response Assessment in Neuro-Oncology) criteria.

Primary Endpoints of the pediatric sub-study:

Safety including toxicities according to CTCAE criteria (Percentage of subjects with adverse events from subject's first visit until 49 days after the subject's last dose of study drug)

Pharmacokinetic parameters for ABT-414 and cys-mcMMAF (Maximum observed serum concentration (C_{max}) for ABT-414 and Cys-mcMMAF (toxin), half-life for ABT-414 and Cys-mcMMAF (toxin), and total drug exposure over time (AUC: Area Under the Curve) for ABT-414 and Cys-mcMMAF (toxin)

Secondary Endpoints of the pediatric sub-study:

Objective response rate, best response rate, and duration of response based on RANO criteria

Overall survival, Time to Progression, and Time to progression-free survival

Changes in neurological status and functioning (including PedsQL cancer module)

Exploratory Endpoints of the pediatric sub-study:

Assessment for tumor aberrations of H3.1, H3.3, BRAF, CDKN2A/B, IDH1, INI1, MGMT, PTEN.

Anti-drug antibodies

Methodology:

This is an uncontrolled, open-label, single-arm global study.

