Although not required for study eligibility, the following guidelines should be followed whenever possible to maximize the likelihood that tumor assessments yield data interpretable for tumor response assessment:

If the subject has been operated upon for recurrence:

Residual and measurable disease after surgery is not required, but surgery must have confirmed recurrence

A post-surgery MRI should be available following surgery and an additional MRI scan (baseline scan) has to be done within 2 weeks prior to the first dose of ABT-414.

Surgery completed at least 2 weeks before the first dose of ABT-414 and subjects should have fully recovered as assessed by investigators. Criteria for full recovery will include absence of active post-operative infection, recovery from medical complications and capacity for fluid and food intake.

Dosage of steroids is stable or decreasing for 7 days prior to the baseline MRI scan.

Randomization: Subjects will not be randomized. All subjects will receive ABT-414 at a starting dose of 1.0 mg/kg (age 6-17) or 1.3 mg/kg (age 0 - 5). Treatment should start within 96 hours from enrollment. No stratification will be used.

Study Procedures:

The subjects will follow the same study procedure table as described in the adult protocol (refer to Chapter 6), with the exception of research blood samples, ocular assessments, and long term follow up as described in this appendix.

The PK schedule for 3 to 17 year olds will be as follows:

	Cycle 1 Day 1	Cycle 1 Day 2	Cycle 1 Day 3	Cycle 1 Day 5	Cycle 1 Day 8	Cycle 1 Day 15	Cycle 2 Day1	Cycle 3 Day 1	Cycle 5, Cycle 7 etc. Every two cycles starting from Cycle 5	35 Day Safety Follow- up
PK – ABT-414 Assay	X ^a	X ^b	X ^c	X ^d	X ^e	X ^f	X ^f	X ^f	X ^g	X ^h
PK – Cys-mc MMAF Assay	X ^a	X ^b	X ^c	X ^d	X ^e					
PK Antidrug Antibody Assay (ADA/nADA)	X ^g						X ^g	X ^g	X ^g	X ^h

The PK schedule for < 3year old will be as follows:

	Cycle 1 Day 1	Cycle 1 Day 8	Cycle 1 Day 15	Cycle 2 Day1	Cycle 3 Day 1	Every four cycles starting from Cycle 5	35 Day Safety Follow-up
PK – ABT-414 Assay	X ⁱ	X ^e	X ^f	X ^g	X ^g	X ^g	X ^h
PK Antidrug Antibody Assay (ADA/nADA)	X ^g			X ^g	X ^g	X ^g	X ^h

a. Samples will be collected before infusion (0 hour, pre-dose), immediately after ABT-414 infusion, and 4 hr after the start of infusion.

b. One sample at the 24-hour time point only

c. One sample at the 48-hour time point only (within ± 4 hours)

d. One sample at the 96-hour time point only (within ± 24 hours)

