e. One sample at the 168-hour time point only (within ± 4 hours)

f. Samples will be collected before infusion (0 hour, pre-dose) and immediately after ABT-414 infusion

g. Samples will be collected before infusion (0 hour, pre-dose)

h. Samples will be collected 35 days (within a two-day window) after last ABT-414 infusion for subjects able to return to the clinic for the follow-up visit.

i. Samples will be collected immediately after ABT-414 infusion

NOTE:

For 0 - 5 year-old population 1mL of blood for each analyte (ABT-414, cys-mcMMAF) will be collected. For ABT-414, the resulting serum of ~0.5mL will be put into one split and labeled accordingly. For cys-mcMMAF, the resulting ~0.45mL plasma will be equally distributed into two splits. For ADA and nADA 1ml of blood will be drawn and the resulting serum volume of approximately 0.5mL will be split into two tubes and labeled accordingly.

For 6 – 17 year-old population 2 mL of blood will be collected for ABT-414 and the resulting ~1 mL serum will be split into two tubes and labeled accordingly.

1 mL of blood will be collected for cys-mcMMAF and the resulting ~0.45mL plasma will be equally distributed into two splits. For ADA and nADA, 1ml of blood will be drawn and the resulting serum volume of approximately 0.5mL will be split into two tubes and labeled accordingly.

Pharmacogenetic (PG) sample: optional 3mL blood sample collection for all pediatric subjects that consent. If the PG sample is not collected at the Day 1 visit, it may be collected anytime during the study.

MRI scanning frequency will be as described in the adult protocol, but may be less frequent if deemed to be appropriate by the investigator (e.g. subject is unable to tolerate the scanning frequency).

Therapeutic regimens, expected toxicity, dose modifications:

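### The paediatric sub-study makes Cmax, half-life and AUC of cys-mcMMAF primary for all children, but draws no sample for it under age 3 and stops at 168 h of a 14-day interval at ages 3-17

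*Protocol*

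**What the plan says.** **Endpoints.** Protocol Appendix I states the primary objective as "evaluation of safety, tolerability and pharmacokinetics of ABT-414 in a pediatric population < 18 years of age". Its list of primary endpoints gives Cmax for both analytes, then "half-life for ABT-414 and Cys-mcMMAF (toxin), and total drug exposure over time" (AUC), again for both. No age limit is attached to the cys-mcMMAF endpoints, and no interval is given for AUC.

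**Population.** Appendix I reports that, after the juvenile mouse study, "the pediatric sub-study was opened to include patients aged under 3 years".

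**Sampling at ages 3-17.** Under the table introduced by "The PK schedule for 3 to 17 year olds will be as follows", cys-mcMMAF is assayed in Cycle 1 only: pre-dose, end of infusion, 4 h, 24 h, 48 h, 96 h (± 24 h) and 168 h (± 4 h). ABT-414 is also drawn before and after the Day 15 infusion and in later cycles.

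**Sampling under age 3.** The table has rows for ABT-414 and for antidrug antibody, and none for cys-mcMMAF. The blood-volume note after the footnotes says: "For 0 - 5 year-old population 1mL of blood for each analyte (ABT-414, cys-mcMMAF) will be collected".

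**Analysis.** "Pharmacokinetic parameters of ABT-414 and Cys-mcMMAF will be determined by noncompartmental methods". Mixed-effects modelling with adult data is permitted but not required.

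**Adult kinetics.** Protocol section 1.6: "The observed harmonic mean terminal phase elimination half-life of cys-mcMMAF was approximately 4 days". Appendix I gives ABT-414 every 2 weeks.

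**The concern.** A primary endpoint should be obtainable in the population it is stated for. Under age 3 the schedule supplies no cys-mcMMAF data, so the endpoint and the sampling plan do not match.

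At ages 3-17 the difficulty is one of degree. A noncompartmental half-life needs several points on the decline, spread over enough time. Here the last point comes less than two adult half-lives after dosing, and one of the few late points may move by a day either way. The exposure after day 7 has to be projected from that slope. The children already give blood for ABT-414 at the end of the interval, so much of this uncertainty could be avoided at little cost. What is at stake is how well exposure to the free toxin in children can be compared with that in adults.

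**Working it through.** **Plan's own figure.** The protocol gives no figure for the share of AUC that is observed. The nearest is its precision statement: with 6 or more children, the 95% interval for AUC lies within 60-140% of the geometric mean with more than 90% probability. It cannot be reproduced, because no adult CV is given. Requiring t(0.975, n-1) × s/√n ≤ ln 1.4 with 90% probability gives a maximum CV of 23.9% at n = 6 (log scale). If one or two of six children are under 3, cys-mcMMAF has n = 5 or 4 and the maximum falls to 19.6% or 14.7%. This does not show the statement to be wrong.

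**Inputs from the protocol.** Half-life 4 days (adult), so k = ln 2/4 = 0.173 per day; last sample at 7 days; dosing interval 14 days; Day 15 pre-dose = 14 days after the first infusion.

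**Assumed inputs.** Formation half-life 0 to 2 days; residual CV 20% per sample (10% as an alternative). The documents give neither.

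**Step 1, span.** 7/4 = 1.75 half-lives; 7/14 = half the interval.

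**Step 2, immediate formation.** The share of AUC-infinity beyond time t is 2^(-t/4).
- Beyond day 7: 2^(-1.75) = 0.297. Beyond day 14: 2^(-3.5) = 0.088.
- Share of AUC(0-14 d) after day 7: (0.297 - 0.088)/(1 - 0.088) = 0.229.

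**Step 3, first-order formation at rate a.** The share beyond t is (a·e^(-kt) - k·e^(-at))/(a - k).

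| Formation half-life (days) | Peak (day) | AUC-infinity beyond day 7 | Beyond day 14 | AUC(0-14 d) after day 7 |
|---|---|---|---|---|
| 0.25 | 1.1 | 32% | 9% | 25% |
| 0.5 | 1.7 | 34% | 10% | 27% |
| 1 | 2.7 | 39% | 12% | 31% |
| 2 | 4.0 | 51% | 17% | 41% |

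**Step 4, precision of the elimination rate.** Relative SE = 0.20/√Σ(t - mean t)² ÷ 0.173.

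| Days used | Σ(t - mean t)² | Relative SE | With day 14 added |
|---|---|---|---|
| 2, 4, 7 | 12.67 | 32% | 13% (sum 82.75) |
| 4, 7 | 4.5 | 54% | 16% (sum 52.67) |

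The first row applies when the peak comes before day 2, the second when it comes later but still before day 4. With the peak at day 4 itself the log-linear formula does not apply. The ± 24 h window on the 96 h sample moves the two-point figure from 41% (days 3 and 7) to 82% (days 5 and 7).

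**Step 5, simulated noncompartmental half-life** (true value 4 days, last three points, 20,000 replicates). With formation half-life 0.25 days, the 5th-95th percentiles are 3.2-5.5 days at 10% error and 2.6-8.7 days at 20% error. With formation half-life 1 day and 10% error the median is 7.3 days, because the 48 h point then precedes the peak.

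**Step 6, under age 3.** There are no cys-mcMMAF samples, so no Cmax, half-life or AUC.

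**The case against.** The strongest reply concerns ages 3-17. Seven samples over seven days yield Cmax, AUC(0-168 h) and a terminal slope. The protocol never says that AUC runs over 14 days or to infinity, so the percentages above are measured against targets it did not set. They also rest on an adult half-life and on assumed formation rates and assay error. If the peak is early, three points lie on the decline. SAP section 3.0 defers paediatric methods to a separate SAP that is not among these documents and may define AUC and an extrapolation rule. Most of this stands. A reader might infer that the cys-mcMMAF endpoints are not measured at all at ages 3-17; the documents do not support that.

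Two other inferences also go too far. One is that paediatric dose changes depend on cys-mcMMAF: Appendix I ties the sampling to exposure of ABT-414 before it describes dose adjustment, and does not name cys-mcMMAF there. The other is that the 0-5 year note flatly contradicts the under-3 table. The note can be read as a volume that applies wherever a draw is scheduled, which covers ages 3-5. It is ambiguous rather than a clear contradiction.

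The benefit of a Day 15 sample depends on the level still being quantifiable. Section 1.6 puts dose-normalised Cmax of cys-mcMMAF about 400-fold below that of ABT-414 in molar terms, and no quantification limit is given. The pre-dose cys-mcMMAF samples in the adult schedule do not settle this, since the adult analysis is model-based.

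None of this answers the under-3 gap. A separate SAP can define an analysis, but it cannot supply samples that were not drawn.

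**Conclusion.** The point holds, with different force in the two age groups.

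- **Under 3 years:** the primary cys-mcMMAF endpoints cannot be derived from the scheduled samples. The endpoint list is wrong as written for this group. This rests on the tables alone, with no modelling assumption.
- **Ages 3-17:** the endpoints are measurable, but the half-life is imprecise and the exposure after day 7 is extrapolated. If adult kinetics apply, the unobserved share is at least about 30% of AUC-infinity and 23% of AUC(0-14 d), rising to 51% and 41% at the slowest formation assumed. The 32% relative SE for the elimination rate depends on the assumed 20% residual CV and on a peak before day 2. The schedule can be improved cheaply; it is not invalid.

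The undefined AUC interval is a gap in the text for all ages, unless the separate paediatric SAP fills it.

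**What to change.** **Ages 3-17 (cheap improvement).** In the Appendix I table, add the cys-mcMMAF assay to the existing Cycle 1 Day 15 pre-infusion draw, and define the primary AUC as AUC(0-14 days). That interval is then covered by samples, the share of AUC-infinity beyond the last sample falls to about 9-17%, and the relative SE of the elimination rate falls to about 13%, provided the Day 15 level is quantifiable. Because section 5.5.1 allows ± 2 days on Day 15 dosing, also state how AUC is computed when the draw is not exactly at 14 days. Cost: about 1 mL of blood and one assay per child, at a visit where blood is already drawn, and one table cell in the next amendment.

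**Under 3 years (correction).** If no cys-mcMMAF sample is intended, limit the primary cys-mcMMAF endpoints in Appendix I to ages 3-17 and make clear that the 0-5 year volume note applies only where a draw is scheduled. Otherwise, reconcile the under-3 table with that note. Limiting the endpoint is a wording change and adds no blood.

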ABT-414 will be administered at a starting dose of 1.0 mg/kg or 1.3 mg/kg IV (depending on the age) over 30 – 40 minutes or as directed by the administration guidelines every 2 weeks. ABT-414 treatment will continue for up to 12 months. Prophylactic steroid eye drops will be administered as described in the adult protocol. Each subject enrolled will have PK sampling to assess the exposure of ABT-414 in the pediatric population. Pediatric PK data will be assessed on an ongoing basis throughout the study, and the ABT-414 dosage or frequency of dosing may be adjusted for individual pediatric subjects or for all pediatric subjects subsequently enrolled if exposures are substantially outside the range predicted from the adult experience. If the dose is revised for all newly enrolling pediatric subjects, the Sponsor will notify the sites of this new dose as a written communication, and the change in dose will be described in a later amendment to the protocol. ABT-414 has not been studied in children; therefore the expected toxicities are unknown but expected to be similar to the adult experience. Dose modifications from toxicities will follow the recommendations in the adult protocol, with successive dose reductions from 1.0 mg/kg to 0.75 mg/kg to 0.5 mg/kg in 6 – 17 year-olds, and from 1.3 mg/kg to 1.0 mg/kg to 0.67 mg/kg in 0 - 5 year-olds. More aggressive dose reductions are allowed if the investigator believes that it is in the best interest of the subject.

If ABT-414 is used in combination with temozolomide, ABT-414 will be dosed on Day 1 and Day 15 of the temozolomide cycle (assuming a standard regimen of 200 mg/m²/day for 5 days of each 28-day cycle; for other temozolomide schedules, timing of the ABT-414 dosing schedule should be discussed with the medical monitor). Temozolomide will be allowed only if its use is in accordance with local clinical practice. Temozolomide will not be considered an investigational product for the study (unless this is a local requirement). Anti-neoplastic agents other than temozolomide are specifically prohibited during study treatment unless allowed after discussion with the EORTC study chair. Live attenuated vaccines are not allowed during the study treatment period and for a period of 49 days after last ABT-414 administration.

Clinical evaluation, laboratory tests, and follow-up:

The clinical evaluation, laboratory tests and follow up will follow the adult protocol, except as noted below.

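### Under age 3, noncompartmental analysis of three first-interval ABT-414 samples may overstate AUC(0–14 d) relative to older children and gives a half-life too imprecise to interpret; the optional population model should be the stated method

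*Protocol*

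**What the plan says.** All of this is in Protocol Appendix I unless another place is named.

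- **Endpoints.** Maximum concentration, half-life and AUC of ABT-414 are primary endpoints of the pediatric sub-study, with no exception by age.
- **Method.** Statistical considerations states "Pharmacokinetic parameters of ABT-414 and Cys-mcMMAF will be determined by noncompartmental methods", again without an age exception. It then adds an option: "The pediatric pharmacokinetic data may be analysed with adult pharmacokinetic data from other studies in a non-linear mixed effects modelling". No AUC interval, trapezoid rule or rule for the terminal slope is given.
- **Sampling.** Study Procedures has a separate table for the youngest children, introduced by "The PK schedule for < 3year old will be as follows". On Cycle 1 Day 1 the only ABT-414 sample is the one in footnote i: "Samples will be collected immediately after ABT-414 infusion". One sample follows at 168 h, then a pre-dose and a post-infusion sample on Day 15. Later samples are pre-dose troughs and one sample 35 days after the last infusion. Ages 3–17 also have samples at 4, 24, 48 and 96 h after the first dose.
- **Use of the results.** Under the therapeutic regimens heading, ABT-414 dosing may be adjusted, for one child or for all later ones, "if exposures are substantially outside the range predicted from the adult experience".
- **Pediatric SAP.** SAP section 3.0 leaves the sub-study to a separate SAP, which is not among the documents.

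**The concern.** Noncompartmental analysis suits densely sampled profiles. Here it is the prescribed method in the age group with the sparsest sampling, while the method designed for sparse data is optional.

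Two things follow. First, one trapezoid spans the whole week from the peak to Day 8. If concentrations fall quickly at first and slowly later, that trapezoid lies above the curve and AUC comes out too high. The 3–17 schedule follows the early fall and is largely spared, so under-3 exposures could look higher than those of older children because of the method alone. Second, once the peak is set aside, two points remain for the terminal slope. They fit a line exactly and leave no residual degrees of freedom.

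At stake are two primary endpoints and the comparison of under-3 exposure with the adult range, which the protocol links to dosing adjustments.

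**Working it through.** The plan gives no figure for the accuracy of under-3 AUC or half-life, so there is none to reproduce.

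**Inputs from the documents.** Adult terminal half-life 7.5–12 days and mean clearance 0.19–0.37 mL/h/kg (Protocol section 1.6); infusion 30–40 min (35 min used) every 14 days; under-3 sampling at end of infusion, 168 h and 336 h; 3–17 sampling at end of infusion, 4, 24, 48, 96, 168 and 336 h.

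**Assumed, because the documents give no human values.** Central volume 40–75 mL/kg, distribution half-life 12–36 h, assay-plus-residual error 15% per sample.

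**Step 1: AUC(0–14 d) without a distribution phase.** For a single exponential with rate k over a gap h, the linear trapezoid divided by the true area is (kh/2)·coth(kh/2). With h = 7 days:
- half-life 7.5 d: kh = 7 × 0.693/7.5 = 0.647, ratio 1.035; allowing for the infusion, +3.4%
- half-life 12 d: kh = 7 × 0.693/12 = 0.404, ratio 1.014; +1.4%

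The log trapezoid is exact here, so the bias is 0%.

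**Step 2: AUC(0–14 d) with an assumed distribution phase.** One case, per 1 mg/kg: clearance 0.28 mL/h/kg, half-life 9.5 d (228 h), central volume 50 mL/kg, distribution half-life 24 h.
- α = 0.693/24 = 0.0289/h; β = 0.693/228 = 0.00304/h; k10 = 0.28/50 = 0.0056/h; k21 = αβ/k10 = 0.0157/h
- share of the fast phase = (α − k21)/(α − β) = 0.51
- concentrations at the three times: 19.91, 5.96 and 3.53 µg/mL
- linear: 0.5 × 0.583 × 19.91 + 167.4 × (19.91 + 5.96)/2 + 168 × (5.96 + 3.53)/2 ≈ 2967 µg·h/mL
- log: each later segment is h(C1 − C2)/ln(C1/C2), total ≈ 2720
- exact area ≈ 2412

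The bias is 2967/2412 = +23% (linear) and 2720/2412 = +13% (log). The 3–17 schedule on the same curve gives 2460 (+2%) and 2431 (+1%).

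Median bias over grids of such cases:

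| Assumed central volume | Under 3, linear | Under 3, log | 3–17, linear / log |
|---|---|---|---|
| 40–60 mL/kg | about +22% to +24% | about +12% | about +2% / +1% |
| 60–75 mL/kg, clearance and half-life paired | about +11% | about +6% | about +2% or less |

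Single scenarios run from about +2% or less to +78%. The sign was positive in every two-phase case; the size depends on the assumptions.

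**Step 3: AUC to infinity.** In the single-exponential case the share beyond 336 h is 2^(−14/7.5) = 27% to 2^(−14/12) = 45%, so the result leans on the terminal slope. With a two-point slope the error ran from −7% to +47%; with a three-point slope, from −15% to +29%.

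**Step 4: half-life.** The 168 h and 336 h samples are 7 days apart, or 7/12 = 0.58 to 7/7.5 = 0.93 of a half-life. With 15% error the log-scale SD is √ln(1 + 0.15²) = 0.149, and the SD of the log ratio is √2 × 0.149 = 0.211. The relative standard error of the slope is 0.211/0.647 = 33% at 7.5 d and 0.211/0.404 = 52% at 12 d. The 95% range of the estimate is then 4.6 to 20.8 days for a true 7.5. For a true 12 it is 5.9 days to unbounded, because 0.404 − 1.96 × 0.211 is below zero. Adding the end-of-infusion point, which nothing in the plan prescribes, gives 3.4–8.9 days against a true 7.5–12.

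**The case against.** The strongest reply is that the AUC bias is mostly assumption. The documents give no human central volume, distribution phase or trapezoid rule; the only volumes, 79.0–85.7 mL/kg in section 1.6, are from animals. On the documented half-life alone the bias is at most 3.4%. That stands, and it is why the size is given as a range.

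The separate pediatric SAP may already fix the rules, and the model is already foreseen. Both are true. Appendix I nevertheless prescribes the other method and would have to be aligned.

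The practical effect may also be small. The adjustment rule concerns substantial departures, and adult mean clearance alone spans 0.37/0.19 = 1.9-fold. PK is summarised descriptively. This limits the consequence but does not make the method suitable.

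Four stronger readings are tempting, and the documents do not support them:
- *AUC is overstated by a fixed 10–20%.* No such figure follows without assumed kinetics and an assumed rule, and AUC to infinity may be understated.
- *There is no usable half-life.* Without noise, the two-point slope recovered a median 98% of the true half-life (middle half 93–100%, worst 61%). The main problem is imprecision. The 35-day sample and later troughs add information, chiefly to a model.
- *The bias undermines the check of 1.3 against 1.0 mg/kg.* The 1.3 mg/kg dose covers ages 0–5, and children aged 3–5 have the rich schedule.
- *The precision claim for 6 children fails.* The figure of more than 90% holds if the AUC coefficient of variation is at most about 24%. The adult value is not stated, so the claim is neither confirmed nor refuted. A sparse AUC is also not a lost one.

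**Conclusion.** The mismatch between method and sampling is established from the text: noncompartmental analysis without an age exception, three ABT-414 concentrations in the first interval under age 3 against seven at ages 3–17, and two primary endpoints that depend on them.

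The size is conditional. AUC(0–14 d) under age 3 may be overstated by 0 to 3.4% with no distribution phase. The median overstatement is about 6% to 24% under the assumed distribution phase, against about 2% or less for older children. AUC to infinity may err in either direction. Individual half-lives would be too imprecise to interpret, with a relative standard error of the slope of 33–52% if the error per sample is 15%. This supports changing the stated method. It does not show that any particular exposure will be wrong by a known amount.

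**What to change.** In Appendix I, Statistical considerations:
1. Make the mixed-effects model with adult data the stated method, no longer optional, for ABT-414 AUC and half-life in children under 3.
2. In that group, report observed peak and trough concentrations descriptively.
3. Use model-based exposure wherever under-3 exposure is compared with the adult range.
4. Do not pool sparse and rich noncompartmental values.

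Align the separate pediatric SAP with this text.

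The cost is modelling work that the protocol already foresees, plus reliance on adult data for the model structure, which should be acknowledged when the results are reported. No extra blood samples are needed, and no dosing rule changes.
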